19.3.4 Medical Therapy Committee

Chair: [name]

Responsibilities:

- 1. Develop the standard DVT therapy protocol sections of the Manual of Operations;
- 2. Adjudicate standard DVT therapy protocol issues;
- 3. Credential and train the medical co-investigators;
- 4. Monitor use of standard DVT therapy in study subjects; and
- 5. Continuously monitor advances in medical DVT therapy of relevance to the study protocol.

Reporting:

The Medical Therapy Committee Chair will report to the CCC Chair monthly basis.

Version 4.0

19.3.5 Ultrasound Core Laboratory (VasCore at Massachusetts General Hospital)

Chair: [name]

Responsibilities:

- 1. Develop the ultrasound protocol sections of the Manual of Operations;
- 2. Adjudicate ultrasound protocol issues;
- 3. Credential and train the Vascular Ultrasound Laboratories and sonographers;
- 4. Ensure quality control of ultrasound studies;
- 5. Provide central interpretation of ultrasound studies; and
- 6. Work closely with the DCC to develop eCRFs and process ultrasound data.

Reporting:

The Ultrasound Core Laboratory Chair will report to the CCC Chair monthly.

19.3.6 Clinical Centers

Each ATTRACT Clinical Center has a motivated, multidisciplinary team with an endovascular co-investigator (responsible for performing PCDT), a medical co-investigator (responsible for supervising standard DVT therapy in subjects), an emergency medicine physician (responsible for identifying potential subjects with DVT), and the Vascular Ultrasound Laboratory Director (responsible for identifying potential subjects with DVT, providing quality performance and reporting of ultrasound exams, and working with the Ultrasound Core Laboratory to ensure proper data collection). All co-investigators attested in writing to clinical equipoise (that randomization to either treatment is appropriate for subjects who meet the eligibility criteria).

19.4 Data Coordinating Center (Ontario Clinical Oncology Group, McMaster University)

Chair: [name]

Key Personnel: Drs. [name] (Clinical Outcomes Committee Chair), [name] (Lead Biostatistician), [name] (Adjudication Committee Chair)

Responsibilities:

- 1. contribute methodological and biostatistical expertise;
- 2. develop data capture and quality control methods;
- 3. develop eCRFs with the CCC and Core Laboratories;
- 4. develop and securely maintain a study database;
- 5. implement a standardized process that ensures blinded data collection and minimizes bias;
- 6. perform blinded adjudication of clinical and venographic outcomes;
- 7. produce and reconcile site data queries;
- 8. generate specific study reports as requested by study leadership and the DSMB; and

9. provide oversight over the activities at the Health Economic Core Laboratory.

Reporting:

The DCC Chair will report to the Operations Committee and will supervise the DCC committees and the Health Economic Core Laboratory, as described below.

19.4.1 Clinical Outcomes Committee

Chair: [name]

Responsibilities:

1. contribute expertise on the measurement of PTS and QOL and on scoring of the measures;

2. oversee the training of study nurses on use of the PTS and QOL measures.

Reporting:

The Clinical Outcomes Committee Chair will report to the DCC Chair monthly.

19.4.2 Independent Adjudication Committee

Chair: [name]

Responsibility:

Perform blinded adjudication of clinical and venographic outcomes.

Reporting:

The Adjudication Committee Chair will report to the DCC Chair monthly.

19.4.3 Health Economics Core Laboratory

Chair: [name]

Key Personnel: [name]

Responsibilities:

- 1. contribute expertise with health economic analysis to the study design;
- 2. integrate economic data collection into the mainstream activities of each Clinical Center;
- 3. monitor subject use of cost diaries;
- 4. directly collect itemized hospital bills and UB92 summary bills; and
- 5. conduct a cost comparison and estimate the incremental cost-effectiveness of the two treatment strategies.

Reporting:

The Health Economic Core Laboratory Chair will report to the DCC Chair monthly.

Appendix 2: Flow Chart - Single-Session PCDT

* The rt-PA may be delivered via a standard catheter, the sheath, the Trellis (Technique A patients only), or the Angiojet (Technique B patients only). The total dose for the initial procedure session may not exceed 25mg. The total rt-PA infusion time (not counting periods when the rt-PA infusion is turned off) cannot exceed 24 hours.

** The total rt-PA dose for all treatment sessions together may not exceed 35mg.

Appendix 3: Flow Chart - Infusion-First PCDT

* The rt-PA may be delivered via a standard catheter or the vascular sheath.

** The total rt-PA dose for all sessions together may not exceed 35mg. The total rt-PA infusion time for the entire treatment (not counting periods when the continuous rt-PA infusion is turned off) may not exceed 30 hours.

Appendix 4: Protocol for Trellis PCDT (Technique A)

- Review the initial venogram and estimate the length of the clotted venous segment. For patients with < 12cm thrombus, select a Trellis-8 Catheter with a 15cm treatment zone. For patients with > 12cm thrombus, select a Trellis-8 Catheter with a 30cm treatment zone.
- 2. Obtain an rt-PA solution from the pharmacy: 25mg rt-PA in 25ml Sterile Water (1 mg/ml).
- 3. Calculate the initial rt-PA dose to be delivered into the thrombus according to the following formula: 1mg per 3-4cm thrombus length (which equals 0.25 0.33mg rt-PA per cm thrombus length), with a minimum dose of 4mg. For patients with thrombus exceeding 24cm, two runs of the Trellis-8 Catheter are needed to optimally distribute and disperse the rt-PA within the entire thrombosed venous segment the initial rt-PA dose should be divided proportionally to evenly distribute the drug within the thrombus. For example, for a patient with 36cm of venous thrombus, if the physician chooses to use rt-PA at 1mg per 3cm thrombus length, the total dose would be 12mg. This could be divided evenly between the cephalad (6mg) and caudal (6mg) segments.
- 4. Prepare the rt-PA solution needed for the first run of the Trellis-8 Catheter as follows: Place the rt-PA intended for the first run of the Trellis-8 Catheter into a 10ml syringe, and dilute to a total volume of 10ml in normal saline. For the 15cm Trellis-8 Catheter, which is only used when the thrombus length is 12cm or less, this will result in 4mg rt-PA per run. For the 30cm Trellis-8 Catheter, this will typically result in 3-8mg per run (corresponding to 12 24cm thrombus length). As the total volume to be injected for each run will always be 10ml, the concentration of the injected rt-PA solution will therefore range from 0.3 0.8 mg/ml rt-PA.
- 5. Advance the Trellis-8 Catheter over the guidewire and position its cephalad balloon just above the highest extent of the thrombus. Inflate the cephalad and caudal balloons with dilute contrast, taking care not to over-inflate past the radiopaque markers on the Catheter.
- 6. Perform a stepped infusion of rt-PA into the thrombus. First inject 2ml of rt-PA solution into the infusion port of the Trellis-8 Catheter this will instill 1ml of the rt-PA solution into the thrombus, with an additional 1ml filling the Catheter lumen. Activate the Dispersion Wire of the Trellis-8 for 10 minutes. During oscillation, inject 1ml of the rt-PA solution every minute (after 9 minutes, inject 1ml normal saline to clear the Catheter of rt-PA). Every minute, move the translation bar on the Oscillation Drive Unit to disperse the rt-PA within the clot.

- 7. After 10 minutes have passed, reduce the speed of the Dispersion Wire to one-third of full speed. De-activate and remove the Dispersion Wire and allow the rt-PA to dwell for an additional 5 minutes. Deflate the caudal balloon. At the physician's discretion, the rt-PA remaining within the isolated treatment zone may be aspirated via a syringe applied to the aspiration port of the Trellis-8 Catheter. Deflate the cephalad balloon. If the initial thrombus extent was less than or equal to 24cm, remove the Trellis-8 Catheter over a guidewire.
- 8. If the initial thrombus extent exceeded 24cm, re-position the Trellis-8 caudally to include the remaining thrombus and repeat Steps 4-7 above using the rt-PA planned for the second run. Remove the Trellis-8 Catheter over a guidewire and repeat the venogram.
- 9. If residual thrombus is present, an additional 10-minute run (with 5-minute dwell) of the Trellis-8 may be performed in each of the 1-2 treated segments using the method in Steps 4-8 above (additional rt-PA dose chosen by physician but the rt-PA must be dissolved in 10 ml solution and the physician may not exceed the 25mg rt-PA dose limit for the initial PCDT session). Note: for any single session, the Trellis activation time may not exceed 30 minutes in a single treatment area or 60 minutes overall for multiple treatment areas.
- 10. If needed, consult the Trellis Peripheral Infusion System Instructions for Use (package insert) for additional clarification on the appropriate use of the Trellis system.
- 11. See Section 7.3.1 for details on concomitant heparin use during use of Technique A.
- 12. Return to **Section 7.3.5**. Please note that Technique A patients may receive no more than 24 hours of rt-PA infusion after the initial PCDT session.

Appendix 5: Protocol for AngioJet PCDT (Technique B)

- Review the initial venogram and estimate the length of the clotted venous segment. Prepare an AngioJet DVX or Solent Proxi Catheter as prompted by the Angiojet Drive Unit.
- 2. Obtain an rt-PA solution from the pharmacy: 25mg rt-PA in 25 ml Sterile Water (1 mg/ml).
- 3. Calculate the initial rt-PA dose to be delivered into the thrombus according to the following formula: 1mg per 3 4cm thrombus length (which equals 0.25 0.33mg rt-PA per cm thrombus length), with a minimum dose of 4mg. Assuming that the thrombus length varies between 3 60cm among different patients, this will result in rt-PA doses of 4 20mg. For example, for a 36cm venous segment, if the physician chooses to use 1mg per 3cm thrombus length, the dose would be 12mg.
- 4. Deliver rt-PA into the thrombus using either the PowerPulse or Rapid Lysis methods:
- 5. PowerPulse method: Prepare the rt-PA solution as follows: Dilute the planned rt-PA dose to a total volume of 50 100ml (determined by the physician) in normal saline (this will result in a rt-PA concentration ranging from 0.04 0.40 mg/ml). Put the AngioJet Drive Unit into PowerPulse mode. Advance the AngioJet Catheter over the guidewire and position it just above the cephalad aspect of the thrombus. Pulse-spray the rt-PA into the thrombus by depressing the foot pedal during slow withdrawal and advancement of the AngioJet Catheter through the thrombus (1cm every 3 seconds) over the wire. Allow the rt-PA to dwell within the thrombus for 30 minutes. Proceed to Step 5.
- 6. Rapid Lysis method: Prepare the rt-PA solution as follows: Dilute the planned rt-PA dose to a total volume of 250-500ml (determined by the physician) in normal saline (this will result in a rt-PA concentration ranging from 0.008 0.080 mg/ml). Advance a standard hockey-stick shaped guide catheter over the guidewire and position it just above the cephalad extent of the thrombus. Put the AngioJet Drive Unit into Aspiration mode. Advance the AngioJet Catheter through the guide catheter. Using the rt-PA solution as the infusate, activate the AngioJet Catheter during slow withdrawal and advancement of the AngioJet Catheter and guide catheter during slow withdrawal and advancement of the thrombus (about 1cm every 3 seconds) over the wire. Proceed to Step 5.
- 7. With the AngioJet Drive Unit in Aspiration Mode, activate the AngioJet to aspirate
thrombus by depressing the foot pedal during slow withdrawal and advancement of the AngioJet Catheter through the thrombus over the guidewire. To increase access of the AngioJet Catheter to thrombi located peripherally within the vein, the use of a standard hockey-stick shaped guiding catheter to orient the device during aspiration is encouraged. Perform two back-and-forth passes of the AngioJet Catheter through the thrombus, then remove it.

- 8. Caution: During the procedure, if using a DVX Catheter, do not retract the guidewire into the DVX Catheter. If retraction of the guidewire into the DVX Catheter occurs, remove the DVX Catheter and guidewire from the patient and back-load the DVX Catheter over the guidewire. This will prevent the wire tip from exiting and binding in the Catheter windows. Also, when using the AngioJet in the iliac vein and/or IVC, physicians are encouraged to include rest periods of at least 10 seconds after every 30 seconds of device activation time.
- 9. The total rt-PA dose for the initial session may not exceed 25mg. The AngioJet activation time and infusate volume should not exceed 8 minutes and 500ml, respectively.
- 10. If needed, consult the Instructions for Use (package insert) for the AngioJet System, DVX Catheter, and/or Solent Proxi Catheter for additional clarification on their appropriate use.
- 11. See Section 7.3.1 for details of concomitant heparin use during use of Technique B.
- 12. Return to **Section 7.3.5**. Please note that Technique B patients may receive no more than 24 hours of rt-PA infusion after the initial PCDT session.

Appendix 6: Protocol for Infusion-First PCDT (Technique C)

- 1. Review the initial venogram and estimate the length of the clotted venous segment. Advance a multisidehole catheter into position with its sideholes spanning the thrombus.
- 2. Obtain the following rt-PA solution from the pharmacy: 10mg rt-PA in 10 ml Sterile Water for Injection, USP, diluted to a total volume of 1000 ml in 0.9% normal saline (rt-PA concentration 0.01 mg/ml). Infuse through the multisidehole catheter at a rate of 50-100 ml/hr (corresponding to 0.01 mg/kg/hr, with maximum allowable dose 1.0 mg/hr). For patients in whom fluid volume is of concern or in whom an ultrasound infusion catheter is selected, the physician may concentrate the rt-PA solution to 0.02 mg/ml 0.04 mg/ml (10mg rt-PA in 250-500 ml total volume, infused at 12.5 50 ml/hr). If more than one venous access site is used, the rt-PA dose may be split per physician discretion. The physician may also utilize the vascular sheath (with or without added sideholes) to infuse part of the rt-PA. All infusion catheters should be used per their Instructions for Use (package insert).
- 3. During infusion CDT, the patient should be placed at bedrest and the affected leg should be elevated. Mechanical compression adjuncts may be used per the physician's standard practice. If UFH is used, it should be infused at subtherapeutic levels (6-12 units/kg/hr, maximum allowable dose 1000 units/hr) through the vascular sheath (preferably) or through a peripheral IV (if the sheath is being used to infuse rt-PA), to a target PTT of less than 2 times control. The patient should be monitored in an ICU or stepdown unit and peripheral blood taken at least every 12 hours for hemoglobin, partial thromboplastin time (PTT), and platelet count. A fibrinogen level may be obtained if this is the physician's standard practice.
- The rt-PA infusion may be halted temporarily or permanently at physician discretion if there is evidence of bleeding (see Section 7.3.4), the PTT > 100 seconds, or the fibrinogen level < 100 mg/dl. When rt-PA is stopped, saline should be infused to maintain catheter patency.
- After 6-24 hours, the patient should return to the procedure suite. At each return visit, follow the procedures described in Section 7.3.5. In particular, the use of rheolytic thrombectomy is encouraged at the first follow-up visit to speed thrombolysis (see Appendix 5, Steps 5-9).
- 6. Technique C patients may receive no more than 30 hours of rt-PA infusion.

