1.6.3 CDT Studies with "Low-Dose" Recombinant t-PA

The use of "low-dose" (≤ 2 mg/hr) intrathrombus rt-PA infusions to treat proximal DVT has been described in several studies: **(A)** In a 2001 study by Shortell et al, low-dose rt-PA infusions (2 mg/hr with a maximum dose of 100mg) via CDT provided > 50% clot lysis as often (77% versus 81%, p = NS) and faster (30 hours versus 43 hours) than urokinase (240,000 units/hr for 4 hours)

then 120,000 units/hr) in acute DVT patients (n = 31) (56). (B) In 2003, Sugimoto et al found that catheter-directed infusions of low-dose rt-PA (1 mg/hr) and urokinase (120,000 units/hr) had equal efficacy (≥ 50% clot lysis in 88% versus 83%) and safety (major bleeds 4% in both groups) for treatment of DVT (n = 54) (57). rt-PA infusions were faster (24 hours versus 33 hours, p = 0.011) and less costly (\$418 versus \$6032, p < 0.0001). (C) In 2004, Grunwald et al found rates of clot lysis (97% for rt-PA) and complications (3% for rt-PA) to be comparable for rt-PA (0.5-1.0 mg/hr), urokinase (mean dose 113,000 units/hr), and reteplase (0.5-1.0 unit/hr) in a non-randomized study of 82 DVT patients (58). Drug costs were lower for rt-PA (\$488) than reteplase (\$1787) or urokinase (\$6577) (p < 0.05). Based upon these studies, the SIR subsequently recommended rt-PA dosing of 0.5 - 1.0 mg/hr in its 2006 guality improvement guidelines for endovascular DVT interventions (63). (D) In 2008, Kim et al reported the use of intrathrombus rt-PA infusions to treat 178 patients with DVT (59). Successful (> 50%) clot lysis was observed in 92% of treated limbs, with major bleeding in 4% of patients. Bleeding complications were more common in patients \geq 70 years of age. Notably, there was no intracranial or fatal bleeding in these four studies. Hence, lowdose rt-PA infusions via CDT have been reasonably safe and have produced clot lysis at rates (81-97%) that have far exceeded those of systemic rt-PA delivery.

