6.2.3.3 Technique C (Infusion-First PCDT)

A multisidehole infusion catheter will be positioned within the thrombus with its infusion segment spanning the extent of thrombus (56-63). Use of an endhole-only catheter is not permitted. A rt-PA solution will be continuously infused into the thrombus via the catheter. The subject will be monitored in an ICU or stepdown unit and will undergo follow-up venography within 6-24 hours.

Initial rt-PA Infusion:	0.01 mg/kg/hr (maximum 1.0 mg/hr for 30 hours)
Maximum Allowed rt-PA Dose:	35mg total (includes initial infusion & later doses)
Concomitant Heparin:	LMWH or subtherapeutic UFH (6-12 units/kg/hr,
	maximum dose 1000 units/hr, target PTT less than 2
	times control (no minimum PTT)), target anti-Xa activity

level less than 0.5 IU/ml anti-Xa (63,90)

Step-by-step Protocol: See Section 7 and **Appendix 6**

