6.2.5 Allowed Adjunctive Endovascular Techniques

The following adjunctive endovascular techniques may be used, per the guidelines below, as they are widely used in standard clinical practice to enhance the delivery of rt-PA into the clot or to prevent complications of PCDT (specifically, pulmonary embolism and early re-thrombosis):

 Retrievable IVC Filters: Retrievable IVC filters are commonly used by endovascular physicians to prevent peri-procedural PE in selected patients undergoing PCDT. In a large prospective registry of proximal DVT patients undergoing infusion CDT (without mechanical thrombectomy), symptomatic PE occurred in only 1.3% (49). Therefore, IVC filter placement is discouraged in patients undergoing Infusion-First PCDT (Technique C). However, for patients being treated with single-session PCDT (Techniques A and B, which involve more clot manipulation), there is sparse data to support or refute the use of IVC filters and limited evidence suggests that major PE can occur as a PCDT complication (67,68,87). Therefore, in ATTRACT, a retrievable Tulip filter (Cook Inc., Bloomington, IN) may be used at physician discretion if there is IVC and/or iliac vein thrombus and singlesession PCDT is being used.

- 2. Balloon Maceration, Aspiration Thrombectomy, Rheolytic Thrombectomy, and Infusion CDT: As in routine clinical practice, after initial PCDT the physician may inflate a standard angioplasty balloon within any residual thrombus to macerate it and increase its surface area in order to enable rt-PA delivery to otherwise-inaccessible parts of the thrombus (63). A standard 7-8 French catheter and/or the AngioJet Rheolytic Thrombectomy System may be used to aspirate residual venous thrombus in order to improve flow and thereby prevent the complication of early re-thrombosis. Additional rt-PA bolus doses (up to 5mg per session) may be given. If there is still significant obstructing thrombus after the use of these measures, the physician may initiate (or for Technique C patients, continue) a continuous rt- PA infusion via a multisidehole infusion catheter at 0.01 mg/kg/hr (maximum allowable dose 1.0 mg/hr) for a maximum of 24 hours for Techniques A and B, or for a total maximum infusion time (including previous infusion) of 30 hours for Technique C. In all cases, the total rt-PA dose given for the entire treatment (all sessions together) may not exceed 35mg.

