 (1) via injection through the vascular sheath or a multisidehole catheter; (2) in Technique A patients only, via the Trellis as described in Appendix 4, Steps 4-8; or (3) in Technique B patients only, via the Angiojet (PowerPulse or Rapid Lysis method) as described in Appendix 5, Step 4.
- 3. Perform a repeat venogram. If significant residual obstructing thrombus is present, position a multisidehole infusion catheter within the thrombus and perform Infusion CDT (rt-PA at 0.01 mg/kg/hr, maximum dose 1.0 mg/hr) as outlined in **Appendix 6**. (For Technique C subjects, this will simply represent a continuation of the initial rt-PA infusion.) The rt-PA infusion should continue until near-complete (> 90%) thrombolysis is observed, clinically-overt bleeding becomes evident, or until a maximum of 24 hours (for Technique A or Technique B) or 30 hours total (for Technique C) of rt-PA infusion has occurred.
- 4. The steps in Section 7.3.5 may be repeated as needed, but the above limits on rt-PA dose, infusion duration, device activation time, and AngioJet infusate volume must be followed.

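### Appendix 6 gives one pump-rate range for concentrated rt-PA bags of different strengths, and its upper part exceeds the protocol's 1.0 mg/hr maximum for every bag stronger than 0.02 mg/ml

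*Protocol*

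**What the plan says.** Appendix 6 step 2 starts with a standard bag of 10 mg rt-PA in 1000 ml, which is 0.01 mg/ml. Its pump instruction is "Infuse through the multisidehole catheter at a rate of 50-100 ml/hr", which the step describes as "corresponding to 0.01 mg/kg/hr, with maximum allowable dose 1.0 mg/hr".

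The next sentence allows a stronger solution: "For patients in whom fluid volume is of concern or in whom an ultrasound infusion catheter is selected", the physician may prepare 0.02 to 0.04 mg/ml. The parenthesis that follows reads "10mg rt-PA in 250-500 ml total volume, infused at 12.5" to 50 ml/hr. (The dashes in the strength and rate ranges are lost in the extracted text; the reading is not in doubt.) There is no table, formula or pairing that ties a rate to a strength, and the hourly maximum is not repeated for the concentrated bag.

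The same limit stands elsewhere. Section 6.2.3.3 gives "0.01 mg/kg/hr (maximum 1.0 mg/hr for 30 hours", with 35 mg as the total. Section 6.2.5 item 2 and the synopsis carry the same hourly figure. Section 7.3.5 item 3 sends infusions for residual thrombus to Appendix 6 at "rt-PA at 0.01 mg/kg/hr, maximum dose 1.0 mg/hr", so Appendix 6 also serves subjects who started on Technique A or B.

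**The concern.** A range in ml/hr has one job: to turn a dose limit in mg/hr into a pump setting. That only works if the strength in the bag is fixed or the rate is tied to it. Here the strength may vary two-fold while the rate range stays the same, so a setting that is correct for the weakest permitted bag can be double the limit for the strongest.

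The protocol treats the hourly rate as a bleeding issue. Section 1.6.2 reports more bleeding, by anecdote, with early regimens of 2-5 mg/hr, and Section 1.6.3 notes that "the SIR subsequently recommended rt-PA dosing of 0.5 - 1.0 mg/hr". At stake is the hourly thrombolytic exposure of subjects given a concentrated bag stronger than 0.02 mg/ml. The total dose allowed is not affected.

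**Working it through.** **Inputs.** From Appendix 6 step 2: standard bag 10 mg in 1000 ml at 50-100 ml/hr; concentrated bag 10 mg in 250-500 ml (0.02-0.04 mg/ml) at 12.5-50 ml/hr; maximum 1.0 mg/hr. The maximum is confirmed in Sections 6.2.3.3, 6.2.5 and 7.3.5.

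**Formulas.** Strength (mg/ml) = 10 / volume (ml). Dose rate (mg/hr) = strength x pump rate (ml/hr). Highest compliant pump rate (ml/hr) = 1.0 / strength.

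**Standard bag, reproduced.** 10/1000 = 0.01 mg/ml; 0.01 x 50 = 0.5 and 0.01 x 100 = 1.0 mg/hr. The range tops out exactly at the maximum, so no rate inside it can exceed 1.0 mg/hr.

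**Concentrated bag, where the range comes from.** To deliver the same 0.5-1.0 mg/hr:

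- at 0.02 mg/ml (500 ml): 0.5/0.02 = 25 to 1.0/0.02 = 50 ml/hr
- at 0.04 mg/ml (250 ml): 0.5/0.04 = 12.5 to 1.0/0.04 = 25 ml/hr

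The outer limits of the two together are 12.5-50 ml/hr, the printed range. Each part is right for its own bag; the merged range is not right for both.

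**What the printed range delivers.** The 0.025 and 0.03 mg/ml rows are illustrative strengths inside the permitted span (400 and about 333 ml). The last column is (50 - highest compliant rate) / (50 - 12.5).

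| Strength (mg/ml) | Dose at 12.5 ml/hr (mg/hr) | Dose at 50 ml/hr (mg/hr) | Highest compliant rate (ml/hr) | Part of 12.5-50 above the maximum |
|---|---|---|---|---|
| 0.02 | 0.25 | 1.00 | 50 | 0/37.5 = 0% |
| 0.025 | 0.31 | 1.25 | 40 | 10/37.5 = 27% |
| 0.03 | 0.375 | 1.50 | 33.3 | 16.7/37.5 = 44% |
| 0.04 | 0.50 | 2.00 | 25 | 25/37.5 = 67% |

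The threshold is exact: 0.02 x 50 = 1.0, so any stronger bag has an upper part of the range above the maximum.

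**Does printed order settle the pairing?** No. Matching the ends of the rate range to the ends of the volume range gives 0.04 x 12.5 = 0.5 mg/hr (250 ml) and 0.02 x 50 = 1.0 mg/hr (500 ml), both acceptable. Matching them to the ends of the strength range gives 0.02 x 12.5 = 0.25 and 0.04 x 50 = 2.0 mg/hr. The sentence gives no reason to prefer one reading.

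**Effect on the total.** At 2.0 mg/hr, 35 mg is reached in 35/2.0 = 17.5 hours. At 1.0 mg/hr, the permitted 30 hours of infusion deliver 30 mg. Appendix 6 asks for return to the procedure suite after 6-24 hours, so an infusion at the wrong rate could reach the total limit before the first return.

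**The case against.** The strongest reply is that no individual figure is wrong and the limit still governs. The dilutions are correct, the maximum stands in the sentence just before, and the dose is ordered in mg/kg/hr, from which the pump rate follows. On that reading the ml/hr range only describes the rates that arise across strengths and weights. The standard bag's range also needs the weight-based order: an illustrative 60 kg subject is due 0.6 mg/hr, or 60 ml/hr, although 100 ml/hr is printed. Further, the percentages above are lengths on a scale and not risks, the number of subjects given a strong bag is not stated, operators are credentialed, and infusion takes place under ICU or stepdown monitoring. Section 1.6.3 itself counts rates up to 2 mg/hr as low dose. The Manual of Operations, which is not at hand, may give paired rates.

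Much of this stands. The protocol never authorises 2.0 mg/hr, a correctly calculated weight-based order cannot exceed 1.0 mg/hr, and the percentages should not be read as probabilities. These points limit the severity. They do not remove the fault: the standard range cannot break the absolute maximum whatever rate is chosen, and the concentrated range can. An instruction that is safe only if the reader recalculates it has failed as a pump instruction.

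One further objection bears on the remedy. Paired ranges with a floor of 0.5 mg/hr do not fit subjects under 50 kg, since 0.5/0.01 = 50. An illustrative 45 kg subject is due 0.45 mg/hr, or 22.5 ml/hr at 0.02 mg/ml, below the paired floor of 25. That favours a formula over paired ranges.

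**Conclusion.** The point holds. For concentrated bags stronger than 0.02 mg/ml, part of the printed pump-rate range exceeds the protocol's own hourly maximum, by up to a factor of two (2.0 against 1.0 mg/hr at 0.04 mg/ml and 50 ml/hr). The fault is unpaired wording, not a wrong dose limit.

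It reaches only subjects given such a bag, in Technique C or in a clean-up infusion after Technique A or B; how many is not stated. The 0.01 mg/kg/hr dose, the 1.0 mg/hr maximum and the 35 mg total remain in force, and no effect on sample size or analysis is shown. That the range merges two correct ranges is an inference from the arithmetic, which the sponsor should confirm. It should be fixed because it is a thrombolytic dosing instruction and the correction is trivial.

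**What to change.** In Appendix 6 step 2, replace the single rate range for the concentrated solution with a rule: pump rate in ml/hr equals the ordered dose in mg/hr divided by the prepared strength in mg/ml, where the ordered dose is 0.01 mg/kg/hr and never more than 1.0 mg/hr. This covers intermediate strengths and subjects under 50 kg.

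If printed ranges are preferred, give 25-50 ml/hr for 10 mg in 500 ml (0.02 mg/ml) and 12.5-25 ml/hr for 10 mg in 250 ml (0.04 mg/ml), with the same two dose conditions stated beside them. The sponsor should confirm that 0.5-1.0 mg/hr is the intended span and check that the Manual of Operations and pharmacy instructions agree.

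The cost is a one-line correction and a notice to pharmacies and sites. It needs no extra subjects, procedures or analyses.
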